### **8.1. Primary Outcome**

The primary outcome is the elapsed time from random treatment assignment to the development of confirmed abnormal glucose tolerance or clinical diabetes among those enrolled in the primary analysis cohort consisting of participants with islet cell autoimmunity and absence of metabolic abnormalities (normal OGTT). The date of the confirmatory abnormal OGTT or diabetes will be considered as the date of reaching these study endpoints. It is expected that abnormal glucose tolerance will be detected prior to diabetes onset by OGTT; however, the presence of diabetes, without a previous abnormal

OGTT, is also considered an endpoint.

While the hydroxychloroquine prevention study is ongoing, any participant who has progressed to abnormal glucose tolerance will have met the primary endpoint criteria. These participants who have developed abnormal glucose tolerance but have not progressed to Stage 3 T1D will have the option to remain in this study without further therapy; they will receive close monitoring and safety assessments until the development of Stage 3 T1D (clinical diabetes) or until they enroll in another clinical trial, whichever comes first.

The study endpoint is realized with either confirmed OGTT criteria for abnormal glucose tolerance or diabetes or clinical criteria for diabetes.

OGTT criteria for abnormal glucose tolerance or diabetes:

The presence of an OGTT consistent with impaired glucose tolerance or diabetes on two sequential dates. A participant with abnormal glucose tolerance or diabetes on an OGTT should undergo a repeat OGTT as soon as possible, but no less than one day apart. Aim to repeat within one month.

The definition of abnormal glucose tolerance is:

- a. Fasting plasma glucose  $\geq 110$  mg/dL (6.1 mmol/L) and  $< 126$  mg/dL (7.0 mmol/L), or
- b. 2 hour plasma glucose  $\geq 140$  mg/dL (7.8 mmol/L) and  $< 200$  mg/dl (11.1 mmol/L), or
- c. 30, 60, 90 minute plasma glucose during OGTT  $\geq 200$  mg/dL (11.1 mmol/L).

Criteria for Diabetes Diagnosis:

- A. Diabetic Ketoacidosis (DKA) or unequivocally symptomatic\* AND at least one of the following:
- 1) Random glucose  $\geq 200$  mg/dl (11.1 mmol/L) OR
  - 2) Fasting Glucose  $\geq 126$  mg/dl (7.0 mmol/L) OR
  - 3) OGTT = diabetic\*\* OR
  - 4) HbA1C  $\geq 6.5\%$ .

\*Unequivocal symptoms: Severe/persistent polyuria, polydipsia and/or significant unexplained weight loss

\*\*A diabetic OGTT is defined as:

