The primary outcome is the elapsed time from random treatment assignment to the development of confirmed abnormal glucose tolerance or diabetes among those enrolled in the primary analysis cohort consisting of subjects with insulin autoimmunity and absence of metabolic abnormalities (normal OGTT).

The study endpoint is realized with either OGTT criteria for abnormal glucose tolerance or diabetes or clinical criteria for diabetes.

OGTT criteria for abnormal glucose tolerance or diabetes:

The presence of an OGTT consistent with abnormal glucose tolerance or diabetes on two sequential dates. A subject with abnormal glucose tolerance or diabetes on an OGTT should undergo a repeat OGTT as soon as possible, but no less than one day apart. Aim to repeat within one month. The time of abnormal glucose tolerance or diabetes will then be taken as the date of the confirmatory abnormal OGTT. The definition of abnormal glucose tolerance or diabetes is:

- a. Fasting plasma glucose ≥ 110 mg/dL (6.1 mmol/L) and < 126 mg/dL (7 mmol/L) or
- b. 2 hour plasma glucose ≥ 140 mg/dL (7.8 mmol/L) and < 200 (11.1 mmol/L), or
- c. 30, 60, 90 minute plasma glucose during OGTT ≥ 200 mg/dL (11.1 mmol/L)

Onset of Diabetes:

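### SAP section 2 labels the AGT-only glucose bands as the definition of AGT or diabetes, so it is unclear whether an AGT test paired with certain diabetic OGTTs is a primary event

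*SAP*

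**What the plan says.** **SAP section 2, Primary Outcome.** The OGTT endpoint rule opens with "The presence of an OGTT consistent with abnormal glucose tolerance or diabetes on two sequential dates". The SAP then writes "The definition of abnormal glucose tolerance or diabetes is" and lists three items joined by *or*:

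- a. a fasting band that runs from 110 up to, but not including, 126 mg/dL
- b. a 2-hour band with the same structure: "2 hour plasma glucose ≥ 140 mg/dL (7.8 mmol/L) and < 200 (11.1 mmol/L), or"
- c. any 30-, 60- or 90-minute value of at least 200 mg/dL, with no upper limit.

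**SAP section 2, Onset of Diabetes.** The diabetic thresholds (fasting ≥126, 2-hour ≥200 mg/dL) appear separately, and a diabetes criterion has to be met on two occasions. The closing sentence dates the endpoint at the second occasion on which either set of criteria is met. Diabetes diagnosed by other criteria goes to adjudication.

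**Protocol 8.1.** The same three-item list appears under "The definition of abnormal glucose tolerance is", with no mention of diabetes in the label. A separate entry, "A diabetic OGTT is defined as", gives fasting ≥126 and/or 2-hour ≥200 mg/dL. The endpoint needs two sequential OGTTs, each consistent with impaired tolerance or diabetes.

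**Protocol 3.3.2, exclusion 1.** Under a heading that covers both AGT and diabetes, the cut-offs are fasting ≥110, or 2-hour ≥140, or a 30/60/90-minute value ≥200 mg/dL, without upper limits.

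**The concern.** Items a and b stop where diabetes begins. That is right for a list that separates AGT from diabetes. It is wrong for a list said to define either state, because some diabetic OGTTs then fail the definition.

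The case that matters is a mixed pair: one OGTT in the AGT range and one diabetic OGTT that meets none of a to c. The list is met once and the diabetes criterion once. If each must be met twice within its own set, there is no primary event, although Protocol 8.1 recognises one.

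This is the primary endpoint, and the two documents could classify the same participant differently. Protocol 7.3 withdraws participants who reach the endpoint from therapy, and Protocol 3.9.2 lets those with AGT stay for monitoring or join another trial. Under the literal SAP reading such a participant would still be event-free, and would later be censored or counted at a later pair of tests. OGTTs are about six months apart (Protocol 4.4) and SAP section 3 groups event times into six-month steps, so a missed confirmation could move an event by at least one step. The counts that trigger the interim (40) and final (80) analyses could also differ between the two documents.

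**Working it through.** **1. Design figure.** Inputs from SAP section 5: 80 events, hazard ratio 0.50, 2:1 allocation, two-sided 0.05. Schoenfeld's formula gives power = Φ(√(d·p(1−p))·|ln HR| − z).

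- √(80 × 1/3 × 2/3) × ln 2 = 4.216 × 0.693 = 2.923
- 2.923 − 1.960 = 0.963, and Φ(0.963) = 0.832
- With the final boundary of 1.969: 0.830

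The stated 83% is reproduced. It does not depend on the wording of the OGTT list.

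**2. The definitions side by side (mg/dL).**

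| Source | Label | Fasting | 2-hour | 30/60/90 min |
|---|---|---|---|---|
| Protocol 8.1 | AGT | 110 to <126 | 140 to <200 | ≥200 |
| Protocol 8.1 | Diabetic OGTT | ≥126 | ≥200 | – |
| SAP section 2 | AGT or diabetes | 110 to <126 | 140 to <200 | ≥200 |
| Protocol 3.3.2, exclusion 1 | AGT or diabetes | ≥110 | ≥140 | ≥200 |

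The SAP carries the label of the fourth row over the numbers of the first.

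**3. Which diabetic OGTTs fall outside the SAP list.** The items are joined by *or*, so all three must fail: fasting not 110–125, 2-hour not 140–199, and every 30/60/90-minute value below 200.

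**4. A hypothetical pair.** OGTT 1 has a 2-hour value of 150 and is otherwise normal. OGTT 2 has fasting 104, 30/60/90-minute values 170/195/198 and 2-hour 204.

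- Protocol 8.1: OGTT 1 is AGT and OGTT 2 is diabetic, so this is an event.
- SAP list: OGTT 1 meets b. OGTT 2 fails a (104 < 110), b (204 is not < 200) and c (all < 200). Met once.
- SAP diabetes rule: only OGTT 2 meets a criterion. Met once.
- Read literally, neither two-occasion rule is satisfied. Reversing the order changes nothing.

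**5. Logic check on a grid.** Take fasting 100, 115 or 130; 2-hour 120, 160 or 220; highest 30/60/90-minute value 180 or 210. That is 3 × 3 × 2 = 18 profiles, of which 10 are diabetic and 7 are AGT only.

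- Three of the 10 diabetic profiles lie outside the SAP list (fasting / 2-hour / highest 30/60/90-minute value): 100/220/180, 130/120/180 and 130/220/180.
- There are 7 × 10 = 70 AGT–diabetic pairs. Under the literal SAP rule 7 × 3 = 21 fail. Under Protocol 8.1 none fails.

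These are grid cells chosen to test the logic. They are not patient frequencies.

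**6. Size, by assumption only.** The documents give no frequency for such pairs. If a share of the 80 events went uncounted and was never replaced, step 1 gives:

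| Share uncounted | Events left | Power |
|---|---|---|
| 0% | 80 | 83.2% |
| 2% | 78.4 | 82.5% |
| 5% | 76 | 81.3% |
| 10% | 72 | 79.2% |

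The final analysis waits for 80 events, so uncounted events would more likely delay it than reduce its power.

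**The case against.** The strongest reply is that the SAP already counts mixed pairs. Its lead sentence asks for OGTTs consistent with AGT or diabetes on two dates, which is essentially the protocol's rule. Its dating sentence comes after both sets of criteria and refers to the second occasion meeting either. In the hypothetical pair, OGTT 2 meets the 2-hour diabetes criterion and so is naturally read as that second occasion. This stands as evidence of intent. It does not settle the matter: the dating sentence fixes a date, and it amends neither the list's definition nor the requirement that a diabetes criterion be met twice.

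The second reply is that few tests are affected. This also stands. Item c has no ceiling, either of the other values may fall within its band, and two diabetic OGTTs still count through the SAP's diabetes rule.

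The third is adjudication. Protocol 8.1 sends cases outside its criteria to the Eligibility and Events Committee, and under Protocol 10.2.4 that masked committee decides uncertain cases. Some mixed pairs might be caught this way. The route is not assured, because the pair is not uncertain under Protocol 8.1, and the SAP's own route is for cases already diagnosed as diabetes.

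A reader might go further and infer that the SAP drops diabetic results altogether, that a known share of events is lost, or that the fastest progressors are removed and the comparison biased. The documents support none of this. The exclusion is partial and depends on a literal reading, no frequency is given, nothing shows how fast the affected participants progress, and the rule is the same in both masked arms.

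**Conclusion.** The concern holds as an inconsistency in the primary endpoint definition. The SAP puts an AGT-or-diabetes label on bands that exclude some diabetic OGTTs. Read literally, an AGT test paired with such a test, in either order, is not a primary event, although Protocol 8.1 makes it one. The SAP's lead and dating sentences point the other way, so the text supports two answers for the same pair.

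The number of events involved cannot be derived from the documents. Zero is possible if the dating sentence governs. That the number is small is a judgement, based on the three conditions that must hold together. The power table rests on assumed shares and on lost events not being replaced. The 80-event target and 83% power are not in question. The point still deserves correction, because the count of primary events should not depend on which sentence of one section is programmed.

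**What to change.** Reconcile SAP section 2 with Protocol 8.1:

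1. Label the bounded list AGT only.
2. Add the protocol's diabetic-OGTT definition (fasting ≥126 and/or 2-hour ≥200 mg/dL).
3. State that any two sequential OGTTs, each AGT or diabetic, make a primary event: AGT/AGT, AGT/diabetic in either order, or diabetic/diabetic. Date the event at the confirmatory test.
4. Use the same rule for the 40-event and 80-event counts.

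An equivalent for items 1 and 2 is to define an OGTT showing AGT or diabetes by the uncapped cut-offs already in Protocol 3.3.2, exclusion 1, and to keep the bounded bands for classifying AGT alone.

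The cost is one wording change and a matching check of the endpoint program, with no new data. It should be made before unblinding. The documents do not show whether that is still possible: the SAP is dated September 2022 and is partly in the past tense. If unblinding has already happened, record the change as a clarification to the rule in Protocol 8.1 and report how many participants it reclassifies.

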### **7.3. Protecting Against or Minimizing Potential Treatment Risks**

Participants who have other active serious medical problems will not be enrolled. Frequent monitoring of participants with history, physical examination, and laboratory studies will allow for early identification of adverse events. Every attempt will be made to minimize the number of venipunctures. Participants will be screened for G6PD deficiency and excluded if present.

To mitigate potential ophthalmologic risk, a fundus photograph or examination will be attempted at Baseline, and OCT and visual field examinations will be attempted annually in all participants. Participants with a successful OCT examination may continue with the study per protocol. If neither the OCT nor visual field examination can be successfully completed (e.g., in very young children), these

examinations will be re-attempted on an annual basis while the participant continues on study drug. The target dose of hydroxychloroquine will be 5.0 mg/kg/day to a maximum of 400mg. This is below the dose associated with ophthalmologic risk. Moreover, individuals who reach study endpoint (abnormal glucose tolerance) will be considered to be a non-responder and withdrawn from therapy, thus decreasing duration of exposure.

Individuals will be informed of potential impact on skin, sleep, gastrointestinal symptoms, and muscle aches. If symptoms continue or are intolerable, drug dose may be temporarily reduced or stopped, at the discretion of the investigator in consultation with the medical monitor. If signs or symptoms are consistent with infectious mononucleosis, evaluation may include measurements of EBV serology and viral load as clinically indicated.

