## 8.2. Primary Analysis

The primary objective of the study is to assess the effect of hydroxychloroquine therapy versus placebo on the risk of progression to Stage 2 or 3 T1D, which is measured from an OGTT or clinically diagnosed with confirmation.

Time to progression to Stage 2 or 3 T1D will be calculated across participants within each treatment group. Time to T1D stage progression will be estimated based on Kaplan-Meier methodology, where participants who were "free of abnormal glucose tolerance and/or T1D" at their last follow-up will be censored at that time point.

This time-to-event outcome will be analyzed using a Cox proportional hazards regression model that stratifies by prior T1D prevention treatment (none vs. placebo vs. active therapy) and age at the time of randomization (<8 yr vs  $\geq$ 8 yr), where treatment effect in this model will be tested using the Wald statistic. Incorporating these as stratification factors in the Cox regression model will allow separate baseline hazard functions to be fitted for each stratum. We will further evaluate differences in event rates in those in the prior treatment stratification factor; specifically, we will assess if there are differential event rates in those enrolling after participation in another prevention trial and ensure that this is accommodated by corresponding stratification in the Cox regression model.

In addition to stratifying on these factors, we will also evaluate if they are effect modifiers on any differences observed in the time to T1D stage progression between these prior treatment groups; i.e., we will formally test for interactions of treatment effect with prior treatment for T1D prevention as well as age on time to T1D stage progression (i.e. progression from Stage 1 to Stages 2 or 3 T1D).

Proportional hazards can be tested to ensure that we can assume that these effects will be parallel. If the assumption of proportional hazard is not appropriate, the data will be examined to determine the cause of non-proportional hazard, such as the presence of a decaying, diverging, or crossing effect of hazard ratios over time. Based on the cause of the non-proportional hazard, post-hoc analyses such as frailty models, parametric models, or models with interactions and time-dependent covariates may be employed.

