Criteria for diabetes_onset (T1DM) are based on glucose testing, or the presence of unequivocal hyperglycemia with acute metabolic decompensation (diabetic ketoacidosis). One of the following criteria must be met on two occasions as soon as possible but no less than one day apart for diabetes to be defined: 1. Symptoms of diabetes plus casual plasma glucose concentration ≥ 200 mg/dL (11.1 mmol/L). Casual is defined as any time of day without regard to time since last meal. The classic symptoms of diabetes include polyuria, polydipsia, and unexplained weight loss. 2. Fasting plasma glucose ≥ 126 mg/dL (7 mmol/L). Fasting is defined as no caloric intake for at least 8 hours. 3. 2 hour plasma glucose ≥ 200 mg/dL (11.1 mmol/L). The test should be performed using a glucose load containing the equivalent of 1.75g/kg body weight to a maximum of 75g anhydrous glucose dissolved in water. It is preferred that at least one of the two testing occasions involve an OGTT. Cases identified will be confirmed as having diabetes if the glucose values to make these determinations were obtained in a TrialNet laboratory as part of an OGTT. Cases diagnosed with diabetes by symptoms and casual glucose ≥ 200 mg/dL or by other criteria than the above will be adjudicated by the TrialNet Endpoint Adjudication Committee.

The date of arriving at the study endpoint is the date of the second occasion that meets either of the above criteria or the date in which the participant presented in a state of DKA.

3. Primary Analysis

The study design is a randomized double-blind placebo-controlled trial. The primary objective of the study is to assess the effect of hydroxychloroquine versus placebo on the risk of developing abnormal glucose tolerance (AGT) as measured from an OGTT.

The cumulative incidence of AGT over time since randomization within each treatment group will be estimated from a Kaplan-Meier estimate of the "AGT-free" survival function. Time-to-AGT was discretized to 6-month times in keeping with the OGTT schedule. The difference between groups in the cumulative incidence functions, and the associated hazard functions, will be tested at the 0.05 level, two-sided, using the Cox regression including age as a covariate (1, 5). The critical value for the test statistic, and confidence intervals in this primary analysis will be determined by the group-sequential procedure.

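### The SAP's primary analysis section tests abnormal glucose tolerance alone, while the rest of the plan counts confirmed abnormal glucose tolerance or diabetes

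*SAP*

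**What the plan says.** **Sections that use the composite**
- SAP section 2, Primary Outcome: "The primary outcome is the elapsed time from random treatment assignment to the development of confirmed abnormal glucose tolerance or diabetes". It allows an OGTT route and a clinical route, and its dating rule also covers presentation in DKA: "The date of arriving at the study endpoint is the date of the second occasion that meets either of the above criteria".
- SAP section 5: the final analysis is triggered by 80 events, each AGT or diabetes.
- SAP section 6: the interim look is triggered by 40 participants with progression to Stage 2 or 3.
- Protocol 8.1: "The study endpoint is realized with either confirmed OGTT criteria for abnormal glucose tolerance or diabetes or clinical criteria for diabetes". It expects AGT to be found "prior to diabetes onset by OGTT; however, the presence of diabetes, without a previous abnormal" OGTT still counts as an endpoint.
- Protocol 8.2: the objective is "the risk of progression to Stage 2 or 3 T1D, which is measured from an OGTT or clinically diagnosed with confirmation".

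**Sections that use AGT alone**
- SAP section 3: the objective is stated as the effect "on the risk of developing abnormal glucose tolerance (AGT) as measured from an OGTT". The Kaplan-Meier curve is for AGT-free survival and the time variable is time to AGT.
- SAP 4.1 to 4.3, and the non-proportionality item under 4.4, refer to risk of, onset of or time to AGT. SAP 4.4 contrasts the AGT endpoint with Type 1 diabetes.
- SAP 7.2: the final-analysis trigger counts confirmed AGT in the placebo group.

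The SAP abbreviation list expands AGT only as abnormal glucose tolerance.

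**The concern.** Section 3 is where a programmer would look to build the primary event variable. As worded, it has no place for diabetes diagnosed clinically or without earlier confirmed AGT. It also does not say whether such a case is an event, a censored observation or a competing event. Under Protocol 3.9.2, a participant who reaches Stage 3 is no longer followed in this protocol, so AGT could not be recorded later. On the literal reading, that participant would be censored at diagnosis. This removes people who progressed furthest from the event count, and the censoring is informative because it is caused by the disease process under study.

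The supporting definitions do not settle the matter:
- The criteria list a to c in SAP section 2 is introduced with "The definition of abnormal glucose tolerance or diabetes is", but it holds the protocol's AGT criteria. Items a and b stop below the diabetic thresholds.
- The SAP's diabetes-onset criteria require two occasions, except for DKA, and include no HbA1c criterion. Protocol 8.1 accepts unequivocal symptoms with one qualifying measure, and certain pairs that include HbA1c.
- The adjudicating committee has a different name in each document.

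**Working it through.** **Side by side.** The AGT wording sits where the protocol has the composite.

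| Topic | Protocol | SAP |
|---|---|---|
| Primary objective | 8.2: Stage 2 or 3, by OGTT or clinical diagnosis | 3: AGT, by OGTT |
| Subgroup tests | 8.3: Stage 2 or 3 | 4.1: AGT |
| Longitudinal markers | 8.3: up to Stage 2 or 3 | 4.3: up to AGT |
| Final-analysis trigger | 8.4: 80 events, AGT or diabetes | 5: the same; 7.2: 64 to 70 AGT events on placebo |

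**Step 1. Reproduce the planned power.** Inputs from SAP 5 and 6: 80 events, hazard ratio 0.50, 2:1 allocation, final critical value 1.969. With allocation factor (2/3)(1/3) = 2/9,

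power = Φ(√(80 × 2/9) × ln 2 − 1.969) = Φ(2.923 − 1.969) = 83.0%.

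With 1.960 the result is 83.2%. The stated 83% reproduces, and it belongs to the composite event.

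**Step 2. Choose a range for the diabetes-first share s.** The documents give none, so this is an assumption. With OGTTs every six months, a constant hazard h per year from AGT to diabetes, and a confirmation lag L in years,

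s = 1 − [(1 − e^(−0.5h)) / (0.5h)] × e^(−hL).

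- The four-year diabetes risk of 68% in Protocol 2.1.2 gives h = −ln(0.32)/4 = 0.285. For lags of 0, 1 and 2 months, s = 6.8%, 9.0% and 11.1%. This is an upper figure. The 68% is measured from confirmed AGT but is applied here from unobserved onset, and every diabetes onset in the interval is counted as lost.
- Assumed lower early hazards of 0.10 to 0.15 per year give s = 2.5% to 6.0%.

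**Step 3. Power if AGT alone is analysed when 80 composite events have occurred:** Φ(√(80(1 − s) × 2/9) × ln 2 − 1.969).

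| s | Events not counted | AGT events | Power |
|---|---|---|---|
| 0 | 0 | 80 | 83.0% |
| 2.5% | 2.0 | 78.0 | 82.0% |
| 5% | 4.0 | 76.0 | 81.0% |
| 7% | 5.6 | 74.4 | 80.2% |
| 11% | 8.8 | 71.2 | 78.5% |

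**Step 4. Duration if the trial waits for 80 AGT events.** That needs 80/(1 − s) composite events. Inputs: placebo hazard −ln(0.60)/2 = 0.2554 per year (40% at two years), hazard ratio 0.50, 135 and 66 participants, accrual of 50 per year to 201, exponential times, and two-year dropout of 0% or 10%. For an arm of size n with event hazard λ, dropout hazard μ, k = λ + μ and accrual period A = 201/50 = 4.02 years, the expected events by time T are

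n(λ/k) × [1 − (e^(−k(T−A)) − e^(−kT)) / (kA)].

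| s | Composite events needed | Years at 0% dropout | Years at 10% dropout | Months relative to 6 years |
|---|---|---|---|---|
| 0 | 80.0 | 5.2 | 5.6 | −9.4 to −4.7 |
| 2.5% | 82.1 | 5.3 | 5.7 | −8.1 to −3.1 |
| 5% | 84.2 | 5.4 | 5.9 | −6.7 to −1.3 |
| 7% | 86.0 | 5.5 | 6.0 | −5.5 to +0.3 |
| 11% | 89.9 | 5.8 | 6.3 | −3.0 to +3.8 |

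**Step 5. The SAP 7.2 trigger.** When 80 composite events are reached, about 36 are expected on placebo (35.6 without dropout, 35.5 with 10%). SAP 7.2 asks for 64 to 70 events in an arm of 66.

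**The case against.** The strongest reply is that AGT is loose shorthand. SAP section 2 is headed as the primary outcome and defines the composite. Section 3 follows it directly without announcing a new endpoint, and the power and interim sections use the composite. Protocol 7.3 abbreviates in the same way: "individuals who reach study endpoint (abnormal glucose tolerance) will be considered to be a non-responder". In SAP 4.4 the AGT endpoint stands where Protocol 8.3 has the composite, so the contrast with Type 1 diabetes fits the shorthand reading too. Protocol 8.2 censors only participants free of AGT and T1D at last follow-up, so a participant with diabetes would not be censored under the protocol.

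This reading is plausible, and it may be what was intended. It does not remove the defect. The restriction to OGTT measurement in section 3 excludes the clinical route, which shorthand for the event name does not explain. No text declares the shorthand. The protocol's censoring rule shows that the literal SAP reading contradicts the protocol.

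Objections about size are fair and stand:
- The diabetes-first share is assumed, and only power was computed. The direction and size of any bias between arms were not.
- Protocol 2.1.2 gives about 40% (38% in its Figure 3) for progression to AGT specifically. If the planning rate is in effect an AGT rate, 80 AGT events arrive at 5.2 to 5.6 years with no delay.
- Item c of the AGT criteria has no upper limit, so some diabetic OGTTs would count as AGT anyway.
- The SAP sends symptomatic casual-glucose cases and diagnoses by other criteria to adjudication, so the differing diabetes criteria mainly affect dating and routing.
- SAP 7.2 is weak evidence of intent. Its hazard ratios of 0.496 and 0.512 reproduce as 64 and 70 total events with 1:1 allocation and 80% power: exp(−2.802/√(64/4)) = 0.496 and exp(−2.802/√(70/4)) = 0.512. That is not this design under either event definition.

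**Conclusion.** The concern holds and should be fixed. The SAP gives the primary event in two incompatible ways, and the AGT-only wording is in the section that specifies the test. The likely numerical cost is limited: a loss of about 1 to 4.5 percentage points of power if AGT alone is analysed at 80 composite events, or little or no extension if 80 AGT events are awaited. These figures rest on an assumed diabetes-first share of 2.5% to 11%, exponential event times and the planned accrual and dropout. The main reason to act is that the event in a confirmatory test should not be open to choice once data are unmasked, and that participants who go straight to diabetes should be counted as Protocol 8.1 says.

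**What to change.** - In SAP sections 3 and 4.1 to 4.4, including the non-proportionality item, replace AGT as the primary event with confirmed AGT or diabetes (Stage 2 or 3 T1D). Keep Stage 3 T1D as the separate secondary endpoint in 4.4.
- In SAP 7.2, use the same composite event and reconcile the 64 to 70 placebo count with the 80-event total in SAP 5.
- In SAP 7.3, state which event is meant by time to T1D.
- Head the a to c criteria list in SAP section 2 as AGT only.
- Reconcile the SAP's diabetes criteria, dating rule and committee name with Protocol 8.1, so that one set governs the analysis.

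The cost is a revision of SAP text before unmasking. Data collection and sample size do not change. Settling the 7.2 trigger needs a decision on the count as well as a change of words.
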